5.5 Pharmacokinetic Assessments

Blood samples for PK can be obtained from a peripheral IV site or central venous access device. PK samples cannot be obtained from the same line used for drug administration or from an IV site above the site used for drug administration. When the drug is infused through a multi-lumen catheter, the alternate lumen should not be used for sampling due to the risk of drug contamination. All post-infusion samples must be collected within $\pm 10\%$ of the defined timepoints in [Table 5.5.1-1](#) and except 1.5 h samples after starting infusion which must be collected within 15 minutes of the timepoint. Further details of blood collection and processing will be provided to the site in the procedure manual.

PK samples are collected from subjects in the ulocuplumab/LDAC combination arms only. Subjects in the LDAC alone arm, who add ulocuplumab to their treatment regimen are not required to participate in PK measurements.

5.5.1 Pharmacokinetics Collection and Processing and ECG Measurements

Serial blood samples will be collected from the dose escalation cohort. Serial blood samples and time-matched ECGs will be collected from a subset of subjects in the expansion cohort (a minimum of 15 subjects per dose level, Serial PK/ECG Subset) whereas sparse blood samples will be collected in the remaining subjects (sparse sampling subset). Serum for all ADA samples will be collected within 30 minutes before dosing.

[Table 5.5.1-1](#) and [Table 5.5.1-2](#) list the sampling schedule to be followed for the assessment of PK, ECG, ADA and RO. Further details of blood collection and processing will be provided to the site in the procedure manual.

Table 5.5.1-1: Ulocuplumab PK and RO Sampling Schedule and ECG Measurements (Escalation Cohort and Expansion Cohort, Serial PK/ECG Subset)

Study Day	Time (Relative to Dosing) Hour	Time (Relative to Dosing) Hour: Min	PK Blood Sample	RO Sample	ADA Sample	ECG ^a
Cycle 1, Day 1	-1.0	-01:00				X
	0 (pre-dose)	00:00	X	X	X	X ^b
	1.0 (end of infusion) ^c	01:00	X	X		
	1.5	01:30	X			X ^b
	2.0	02:00	X			
	3.0	03:00	X			X ^b
	5.0	05:00	X			
Cycle 1, Day 2	24	24:00	X			
Cycle 1, Day 3	48	48:00	X			
Cycle 1, Day 4	72	72:00	X			
Cycle 1, Day 8	0 (pre-dose)	00:00	X	X		
	1.0 (end of infusion) ^c	01:00	X	X		
Cycle 1, Day 15	0 (pre-dose)	00:00	X	X	X	
	1.0 (end of infusion) ^c	01:00	X	X		
Cycle 2, Day 1	0 (pre-dose)	00:00	X	X	X	
	1.0 (end of infusion) ^c	01:00	X	X		
Cycle 2, Day 8	0 (pre-dose)	00:00	X	X		
	1.0 (end of infusion) ^c	01:00	X	X		
Cycle 2, Day 15	0 (pre-dose)	00:00	X	X		X ^b
	1.0 (end of infusion) ^c	01:00	X	X		
	1.5	01:30	X			X ^b
	3.0	03:00	X			X ^b

Table 5.5.1-1: Ulocuplumab PK and RO Sampling Schedule and ECG Measurements (Escalation Cohort and Expansion Cohort, Serial PK/ECG Subset)

Study Day	Time (Relative to Dosing) Hour	Time (Relative to Dosing) Hour: Min	PK Blood Sample	RO Sample	ADA Sample	ECG ^a
Cycle 3-5, Day 1 ^d	0 (pre-dose)	00:00	X	X	X	
	1.0 (end of infusion) ^c	01:00	X	X		
Cycle 3-5, Day 8 ^d	0 (pre-dose)	00:00	X	X		
	1.0 (end of infusion) ^c	01:00	X	X		
Every 4 Cycles after 5, Day 1	0 (pre-dose)	00:00	X		X	
End of Treatment			X		X	
Follow-up ^e			X		X	

^a ECG only for subjects in expansion cohort Serial PK/ECG Subset

^b 12-lead ECGs will be extracted from the Holter recorded flashcards in triplicate within a 10-minute window ending prior to the nominal ECG collection time and before PK draws

^c If infusion has not completed at 1 hour, then draw PK sample immediately after the infusion ends and record time accurately.

^d The Day 1 and Day 8 pre-dose and end of infusion samples to be collected at Cycle 3 and every cycle thereafter until Cycle 5.

^e Follow-up visit should occur no less than 30 days after the end of treatment visit

Table 5.5.1-2: Ulocuplumab PK and RO Sampling Schedule (Expansion Cohort, Sparse Sampling Subset)

Study Day	Time (Relative to Dosing) Hour	Time (Relative to Dosing) Hour: Min	PK Blood Sample	RO Sample	ADA Sample
Cycle 1, Day 1	0 (pre-dose)	00:00	X	X	X
	1.0 (end of infusion) ^a	01:00	X	X	
Cycle 1, Day 8	0 (pre-dose)	00:00	X	X	
	1.0 (end of infusion) ^a	01:00	X	X	
Cycle 1, Day 15	0 (pre-dose)	00:00	X	X	X
	1.0 (end of infusion) ^a	01:00	X	X	
Cycle 2, Day 1	0 (pre-dose)	00:00	X	X	X
	1.0 (end of infusion) ^a	01:00	X	X	
Cycle 2, Day 8	0 (pre-dose)	00:00	X	X	
	1.0 (end of infusion) ^a	01:00	X	X	
Cycle 2, Day 15	0 (pre-dose)	00:00	X	X	
	1.0 (end of infusion) ^a	01:00	X	X	
Cycle 3-5, Day 1 ^b	0 (pre-dose)	00:00	X	X	X
	1.0 (end of infusion) ^a	01:00	X	X	
Cycle 3-5, Day 8 ^b	0 (pre-dose)	00:00	X	X	
	1.0 (end of infusion) ^a	01:00	X	X	
Every 4 Cycles after Cycle 5, Day 1	0 (pre-dose)	00:00	X		X
End of Treatment			X		X
Follow-up ^c			X		X

^a If infusion has not completed at 1 hour, then draw PK sample immediately after the infusion ends and record time accurately.

^b The Day 1 and Day 8 pre-dose and end of infusion samples to be collected at Cycle 3 and every cycle thereafter until Cycle 5.

^c Follow-up visit should occur no less than 30 days after the end of treatment visit.

5.5.2 Pharmacokinetic Sample Analysis

Serum samples will be analyzed for ulocuplumab by a validated immunoassay.

The PK and potential covariate(s) data may be combined with data from other studies.

5.5.3 Labeling and Shipping of Biological Samples

Detailed instructions for the PK blood collection, labeling, processing, storage, and shipping will be provided to the site in the procedure manual.

5.6 ECG Assessments

Safety ECGs will be done for all subjects at screening, during the treatment period and during follow-up as indicated in [Table 5.1-1](#), [Table 5.1-2](#), and [Table 5.1-3](#). All required safety ECGs will be performed on 12-lead ECG equipment used by the sites, per ECG central vendor guidelines.

Serial ECGs will be obtained only from a subset of subjects in the expansion cohort (a minimum of 15 subjects per dose level, Serial PK/ECG Subset) as indicated in [Table 5.5.1-1](#) and should be obtained at each time point listed.

The subjects must be placed in a supine position for 5 to 10 minutes prior to the start of the ECG recording for both safety and serial ECGs. The recorded QTc interval will be measured with Fridericia's correction (QTcF).

All required serial ECGs will be collected on ECG holter monitor equipment provided by the ECG central vendor. The timing of the ECG data collected on the holter monitor is critical to the endpoint of the study and must be performed according the central vendor guidelines. The serial 12-lead ECGs will be extracted from the Holter recorded flashcards in triplicate within a 10-minute window ending prior to the nominal ECG collection time and before PK draws. The serial ECGs will be assessed by the ECG vendor.

The investigative site should document any deviations from the protocol or procedures related to ECG collection or serum sampling. Accurate documentation will lead to proper accounting of the cumulative data and correct final analysis.

5.8 Immunogenicity Assessments

Samples for the analysis of anti-drug antibodies (ADA) to ulocuplumab (immunogenicity) will be collected at pre-dose in all subjects according to the schedules in [Table 5.5.1-1](#) and [Table 5.5.1-2](#). Additional sample handling, labeling, and shipping details will be provided to the site in the procedure manual. Serum samples will be analyzed by a validated immunogenicity assay. Samples are always to be collected prior to the administration of study medication.

ADA samples are collected from subjects in the ulocuplumab/LDAC combination arms only. Subjects in the LDAC alone arm, who add ulocuplumab to their treatment regimen are not required to participate in ADA measurements.

5.9 Outcomes Research Assessments

Not applicable.

5.10 Other Assessments

5.10.1 Additional Research

This protocol will include residual sample storage for additional research (AR).

For All US sites:

Additional research is mandatory for all study participants, except where prohibited by IRBs/ethics committees, or academic/institutional requirements. Where one or more of these exceptions occurs, participation in the additional research should be encouraged but will not be a condition of overall study participation.

- If the IRB/ethics committees and site agree to the mandatory additional research retention and/or collection, then the study participant must agree to the mandatory additional research as a requirement for inclusion in the study.
- If optional participation is permitted and approved, then the study participants may opt out of the additional research retention and/or collection.

For non-US Sites

Additional research is optional for all study participants, except where retention and/or collection is prohibited by local laws or regulations, ethics committees, or institutional requirements.

This collection for additional research is intended to expand the translational R&D capability at Bristol-Myers Squibb, and will support as yet undefined research aims that will advance our understanding of disease and options for treatment. It may also be used to support health authority requests for analysis, and advancement of pharmacodiagnostic development to better target drugs to the right patients. This may also include genetic/genomic exploration aimed at exploring disease pathways, progression and response to treatment etc.

All requests for access to samples or data for additional research will be vetted through a diverse committee of the study sponsor's senior leaders in Research and Development (or designee) to ensure the research supports appropriate and well-defined scientific research activities.

Samples kept for future research will be stored at the BMS Biorepository in Hopewell, NJ, USA or an independent, BMS-approved storage vendor.

- The manager of these samples will ensure they are properly used throughout their usable life and will destroy the samples at the end of the scheduled storage period, no longer than fifteen (15) years after the end of the study or the maximum allowed by applicable law.
- Transfers of samples by research sponsor to third parties will be subject to the recipient's agreement to establish similar storage procedures.

Samples will be stored in a coded fashion, and no researcher will have access to the key. The key is securely held by the Investigator at the clinical site, so there is no direct ability for a researcher to connect a sample to a specific individual.

Further details of sample collection and processing will be provided to the site in the procedure manual.

Table 5.10.1-1: Residual Sample Retention for Additional Research Schedule

Sample Type	Timepoints for which residual samples will be retained
Serum for Pharmacokinetics	All samples
Bone Marrow Aspirate	All samples
Peripheral blood collections (including serum and plasma)	All samples

5.10.2 Cytogenetic and Molecular Assessments

A central laboratory will perform the following:

Baseline cytogenetic testing - bone marrow aspirate chromosome analysis and, if applicable, AML prognostic panel

5.11 Results of Central Assessments

Results of PK and immunogenicity assessments will be provided in aggregate after the end of the study as needed. All serial ECGs will be transmitted to a central laboratory for measurement of intervals and classification of ECG abnormalities.

6 ADVERSE EVENTS

An *Adverse Event (AE)* is defined as any new untoward medical occurrence or worsening of a preexisting medical condition in a clinical investigation subject administered study drug and that does not necessarily have a causal relationship with this treatment. An AE can therefore be any unfavorable and unintended sign (such as an abnormal laboratory finding), symptom, or disease temporally associated with the use of study drug, whether or not considered related to the study drug.

The causal relationship to study drug is determined by a physician and should be used to assess all adverse events (AE). The causal relationship can be one of the following:

Related: There is a reasonable causal relationship between study drug administration and the AE.

Not related: There is not a reasonable causal relationship between study drug administration and the AE.

The term "reasonable causal relationship" means there is evidence to suggest a causal relationship.

Adverse events can be spontaneously reported or elicited during open-ended questioning, examination, or evaluation of a subject. (In order to prevent reporting bias, subjects should not be questioned regarding the specific occurrence of one or more AEs.)

Sponsor or designee will be reporting adverse events to regulatory authorities and ethics committees according to local applicable laws including European Directive 2001/20/EC and FDA Code of Federal Regulations 21 CFR Parts 312 and 320.

6.1 Serious Adverse Events

A *Serious Adverse Event (SAE)* is any untoward medical occurrence that at any dose:

- results in death
- is life-threatening (defined as an event in which the subject was at risk of death at the time of the event; it does not refer to an event which hypothetically might have caused death if it were more severe)
- requires inpatient hospitalization or causes prolongation of existing hospitalization (see **NOTE** below)
- results in persistent or significant disability/incapacity
- is a congenital anomaly/birth defect
- is an important medical event (defined as a medical event(s) that may not be immediately life-threatening or result in death or hospitalization but, based upon appropriate medical and scientific judgment, may jeopardize the subject or may require intervention [eg, medical, surgical] to prevent one of the other serious outcomes listed in the definition above. Examples of such events include, but are not limited to, intensive treatment in an emergency room or at home for allergic bronchospasm; blood dyscrasias or convulsions that do not result in hospitalization.) Potential drug induced liver injury (DILI) is also considered an important medical event. (See [Section 6.6](#) for the definition of potential DILI.)

Suspected transmission of an infectious agent (eg, pathogenic or nonpathogenic) via the study drug is an SAE.

Although pregnancy, overdose, cancer, and potential drug induced liver injury (DILI) are not always serious by regulatory definition, these events must be handled as SAEs. (See [Section 6.1.1](#) for reporting pregnancies).

Any component of a study endpoint that is considered related to study therapy (eg, death is an endpoint, if death occurred due to anaphylaxis, anaphylaxis must be reported) should be reported as SAE (see Section 6.1.1 for reporting details).

NOTE:

The following hospitalizations are not considered SAEs in BMS clinical studies:

- a visit to the emergency room or other hospital department < 24 hours, that does not result in admission (unless considered an important medical or life-threatening event)
- elective surgery, planned prior to signing consent
- admissions as per protocol for a planned medical/surgical procedure
- routine health assessment requiring admission for baseline/trending of health status (eg, routine colonoscopy)
- medical/surgical admission other than to remedy ill health and planned prior to entry into the study. Appropriate documentation is required in these cases
- admission encountered for another life circumstance that carries no bearing on health status and requires no medical/surgical intervention (eg, lack of housing, economic inadequacy, caregiver respite, family circumstances, administrative reason).
- admission for administration of anticancer therapy in the absence of any other SAEs (applies to oncology protocols).

6.1.1 Serious Adverse Event Collection and Reporting

Sections 5.6.1 and 5.6.2 in the Investigator Brochure (IB) represent the Reference Safety Information to determine expectedness of serious adverse events for expedited reporting. Following the subject's written consent to participate in the study, all SAEs, whether related or not related to study drug, must be collected, including those thought to be associated with protocol-specified procedures. All SAEs must be collected that occur during the screening period and within 30 days of discontinuation of dosing.

The investigator should report any SAE that occurs after these time periods and that is believed to be related to study drug or protocol-specified procedure.

An SAE report should be completed for any event where doubt exists regarding its seriousness.

If the investigator believes that an SAE is not related to study drug, but is potentially related to the conditions of the study (such as withdrawal of previous therapy or a complication of a study procedure), the relationship should be specified in the narrative section of the SAE Report Form.

SAEs, whether related or not related to study drug, and pregnancies must be reported to Sponsor or designee within 24 hours, and the head of the study site to comply with procedures of the study site. SAEs must be recorded on the SAE Report Form; pregnancies on a Pregnancy Surveillance Form (electronic or paper forms). The preferred method for SAE data reporting collection is through the eCRF. The paper SAE/pregnancy surveillance forms are only intended as a back-up option when the eCRF system is not functioning. In this case, the paper forms are to be transmitted via email or confirmed facsimile (fax) transmission to:

SAE Email Address: Refer to Contact Information list.

SAE Facsimile Number: Refer to Contact Information list.

For studies capturing SAEs through electronic data capture (EDC), electronic submission is the required method for reporting. The paper forms should be used and submitted immediately, only in the event the electronic system is unavailable for transmission. When paper forms are used, the original paper forms are to remain on site.

SAE Telephone Contact (required for SAE and pregnancy reporting): Refer to Contact Information list.

If only limited information is initially available, follow-up reports are required. (Note: Follow-up SAE reports should include the same investigator term(s) initially reported.)

If an ongoing SAE changes in its intensity or relationship to study drug or if new information becomes available, a follow-up SAE report should be sent within 24 hours to Sponsor or designee using the same procedure used for transmitting the initial SAE report.

All SAEs should be followed to resolution or stabilization.

BMS will be reporting adverse events to regulatory authorities and ethics committees according to local applicable laws including European Directive 2001/20/EC and FDA Code of Federal Regulations 21 CFR Parts 312 and 320. A SUSAR (Suspected, Unexpected Serious Adverse Reaction) is a subset of SAEs and will be reported to the appropriate regulatory authorities and investigators following local and global guidelines and requirements.

6.2 Nonserious Adverse Events

A *nonserious adverse event* is an AE not classified as serious.

6.2.1 Nonserious Adverse Event Collection and Reporting

The collection of nonserious AE information should begin at initiation of study drug. Nonserious AE information should also be collected from the start of a placebo lead-in period or other observational period intended to establish a baseline status for the subjects.

Nonserious AEs should be followed to resolution or stabilization, or reported as SAEs if they become serious (see [Section 6.1.1](#)). Follow-up is also required for nonserious AEs that cause interruption or discontinuation of study drug and for those present at the end of study treatment as appropriate. All identified nonserious AEs must be recorded and described on the nonserious AE page of the CRF (paper or electronic).

Completion of supplemental CRFs may be requested for AEs and/or laboratory abnormalities that are reported/identified during the course of the study.

6.3 Laboratory Test Result Abnormalities

The following laboratory test result abnormalities should be captured on the nonserious AE CRF page or SAE Report Form (paper or electronic) as appropriate:

- Any laboratory test result that is clinically significant or meets the definition of an SAE

- Any laboratory test result abnormality that required the subject to have study drug discontinued or interrupted
- Any laboratory test result abnormality that required the subject to receive specific corrective therapy.

It is expected that wherever possible, the clinical rather than laboratory term would be used by the reporting investigator (eg, anemia versus low hemoglobin value).

6.4 Pregnancy

If, following initiation of the study drug, it is subsequently discovered that a study subject or a partner of a male subject is pregnant or may have been pregnant at the time of study exposure, including 78 days (5 half-lives of study drug plus duration of ovulatory cycle) for a female subject and 138 days (5 half-lives of study drug plus duration of sperm turnover) for a partner of a male subject after product administration, the investigator must immediately notify the Sponsor or designee of this event and complete and forward a Pregnancy Surveillance Form to BMS Designee within 24 hours and in accordance with SAE reporting procedures described in [Section 6.1.1](#).

In most cases, the study drug will be permanently discontinued in an appropriate manner (eg, dose tapering if necessary for subject safety). Please call the Sponsor or designee within 24 hours of awareness of the pregnancy.

In the rare event that the benefit of continuing study drug is thought to outweigh the risk, after consultation with Sponsor/designee, the pregnant subject may continue study drug after a thorough discussion of benefits and risk with the subject.

Protocol-required procedures for study discontinuation and follow-up must be performed on the subject unless contraindicated by pregnancy (eg, x-ray studies). Other appropriate pregnancy follow-up procedures should be considered if indicated.

The investigator must immediately notify the Sponsor or designee of this event and complete and forward a Pregnancy Surveillance Form to Sponsor or designee within 24 hours and in accordance with SAE reporting procedures described in [Section 6.1.1](#).

Follow-up information regarding the course of the pregnancy, including perinatal and neonatal outcome and, where applicable, offspring information must be reported on the Pregnancy Surveillance Form.

Any pregnancy that occurs in a female partner of a male study participant should be reported to Sponsor or designee. In order for BMS to collect any pregnancy surveillance information from the female partner, the female partner must sign an informed consent form for disclosure of this information. Information on this pregnancy will be collected on the Pregnancy Surveillance Form.

6.5 Overdose

An overdose is defined as the accidental or intentional administration of any dose of a product that is considered both excessive and medically important. All occurrences of overdose must be reported as an SAE (see [Section 6.1.1](#) for reporting details.).

[figure not shown]
6.6 Potential Drug Induced Liver Injury (DILI)

Wherever possible, timely confirmation of initial liver-related laboratory abnormalities should occur prior to the reporting of a potential DILI event. All occurrences of potential DILIs, meeting the defined criteria, must be reported as SAEs (see Section 6.1.1 for reporting details).

The criteria for identifying p-DILI events depend on whether the subject's baseline liver biochemistry is normal or abnormal (see Figure 6.6-1).

Potential drug induced liver injury is defined as:

Figure 6.6-1: Algorithm for p-DILI identification and mandatory SAE reporting in subjects with (i) normal baseline liver biochemistry, and (ii) abnormal baseline liver biochemistry

6.7 Other Safety Considerations

Any significant worsening noted during interim or final physical examinations, electrocardiogram, x-ray filming, any other potential safety assessment required or not required by protocol should also be recorded as a nonserious or serious AE, as appropriate, and reported accordingly.

Since ulocuplumab contains only human protein sequences, it is unlikely to be immunogenic and to induce infusion or hypersensitivity reactions. Since this antibody specifically binds to CXCR4, this makes it less likely that such a reaction would occur. However, if such a reaction were to occur, it might manifest with fever, chills, rigors, headache, rash, pruritus, arthralgias, hypo or hypertension, bronchospasm, or other symptoms.

As of the 17-Feb-2014 cut-off date, infusion reactions have been reported in 1 AML subject, 3 CLL subjects and 1 DLBCL subject out of the 86 treated subjects in the CA212001 study and 2 myeloma subjects out of the 42 treated subjects in the CA212002 study.

Prophylactic premedication may be given any time after the first dose of Cycle 1. However, if a subject experiences a Grade 2 infusion reaction, the subject will be required to receive prophylactic premedication for subsequent infusions of ulocuplumab ([Section 3.4.1](#)).

Infusion reactions should be graded according to the NCI CTCAE v4.03 guidelines. Treatment recommendations are provided below and may be modified based on local treatment standards and guidelines, as appropriate:

For Grade 1 symptoms: (Mild reaction; infusion interruption not indicated; intervention not indicated)

Remain at bedside and monitor subject until recovery from symptoms. Information on prophylactic premedications is provided in [Section 3.4.1](#).

For Grade 2 symptoms: (Moderate reaction, requires therapy or infusion interruption but responds promptly to symptomatic treatment [eg, antihistamines, nonsteroidal anti inflammatory drugs (NSAIDs), narcotics, corticosteroids, IV fluids]; prophylactic medications indicated for ≤ 24 hours).

Stop the ulocuplumab infusion, begin an IV infusion of normal saline, and treat the subject with diphenhydramine 50 mg IV (or equivalent) and/or acetaminophen; remain at bedside and monitor subject until resolution of symptoms. Corticosteroid therapy may also be administered as appropriate. If the infusion is interrupted, then restart the infusion at 50% of the original infusion rate when symptoms resolve; if no further complications ensue after 30 minutes, the rate may be increased to 100% of the original infusion rate. Monitor subject closely. If symptoms recur then no further ulocuplumab will be administered at that visit. The amount of study drug infused must be recorded on the case report form (CRF). The following prophylactic premedications are recommended for future infusions: diphenhydramine 50 mg (or equivalent), paracetamol (acetaminophen) and/or corticosteroids should be administered at least 30 minutes before additional ulocuplumab administration. Remain at bedside and monitor subject until recovery from symptoms.

For Grade 3 or Grade 4 symptoms: (Severe reaction, Grade 3: prolonged [ie, not rapidly responsive to symptomatic medication and/or brief interruption of infusion]; recurrence of symptoms following initial improvement; hospitalization indicated for other clinical sequelae [eg, renal impairment, pulmonary infiltrates]. Grade 4: life threatening; pressor or ventilatory support indicated).

Immediately discontinue infusion of ulocuplumab. Begin an IV infusion of normal saline, and treat the subject as follows: Recommend bronchodilators, epinephrine 0.2 to 1 mg of a 1:1,000 solution for subcutaneous administration, 0.3 mg of a 1:1,000 solution for intramuscular administration, or 0.1 to 0.25 mg of a 1:10,000 solution injected slowly for IV administration, and/or diphenhydramine 50 mg IV with methylprednisolone 100 mg IV (or equivalent), as needed. The

subject should be monitored until the investigator is comfortable that the symptoms will not recur. Ulocuplumab will be permanently discontinued. Investigators should follow their institutional guidelines for the treatment of anaphylaxis. Remain at bedside and monitor subject until recovery from symptoms.

In the case of late occurring hypersensitivity symptoms (eg, appearance of a localized or generalized pruritus within 1 week after treatment), symptomatic treatment may be given (eg, oral antihistamine, or corticosteroids).

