3.4 Concomitant Treatments

3.4.1 Permitted Treatments

The following therapies are permitted during the study:

- a) Prophylactic antiemetics may be administered at the discretion of the treating physician prior to all doses of ulocuplumab, except the initial infusion of ulocuplumab in Cycle 1.
- b) If a subject experiences a Grade 2 infusion reaction with ulocuplumab, the subjects will be required to receive the prophylactic premedications for subsequent infusion of ulocuplumab. The pre-medications including, but not limited to, IV or oral diphenhydramine 50 mg (or

- equivalent), acetaminophen 2 x 325 mg orally, and corticosteroids (25 mg of IV hydrocortisone or equivalent) should be administered at least 30 minutes before ulocuplumab administration.
- c) Subjects are permitted to use topical, ocular, intra-articular, intranasal, and inhalational corticosteroids (with minimal systemic absorption). Physiologic replacement doses of systemic corticosteroids are permitted, even if > 20 mg/day prednisone equivalents. A brief course of corticosteroids for prophylaxis (eg, contrast dye allergy) or for treatment of non-autoimmune conditions (eg, delayed-type hypersensitivity reaction caused by contact allergen) is permitted.
 - d) Radiation therapy to choroidomas allowed, but irradiated lesion may not be used to assess response.
 - e) Hydroxyurea can be administered up to Day 21 of Cycle 1, if clinically indicated, at the investigator's discretion as per institutional guidelines.

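### Section 6.7's Grade 2 paragraph stops ulocuplumab only for that visit when symptoms recur after restart, without pointing to the permanent stop that the protocol's printed Grade 3 wording calls for

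*Protocol*

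**What the plan says.** Protocol Section 6.7 gives grade-specific steps for infusion reactions, after the instruction "Infusion reactions should be graded according to the NCI CTCAE v4.03 guidelines".

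- **Grade 2.** The infusion is stopped and the subject treated. If it was interrupted, the site is to "restart the infusion at 50% of the original infusion rate when symptoms resolve", and may return to full rate after 30 uneventful minutes. Then: "If symptoms recur then no further ulocuplumab will be administered at that visit". Apart from an instruction to record the amount infused, the next content is "The following prophylactic premedications are recommended for future infusions".
- **Grade 3 or 4.** The description opens "Severe reaction, Grade 3: prolonged" and includes, as an item set off by semicolons, "recurrence of symptoms following initial improvement". The action is "Ulocuplumab will be permanently discontinued".

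Other sections bear on the same event. Section 4.6.1.1 and Table 4.6.1.2-1 list a Grade 3 or higher infusion reaction as a discontinuation criterion. Section 3.5 makes adverse events that meet Section 4.6.1 a reason for which treatment must stop. Section 1.5 repeats the rule. For a Grade 2 reaction, by contrast, Section 3.4.1 says "the subjects will be required to receive the prophylactic premedications for subsequent infusion of ulocuplumab", and the ulocuplumab infusion note in Table 5.1-2 says the same in substance.

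**The concern.** A nurse or investigator managing a Grade 2 reaction works from the Grade 2 paragraph. When symptoms return after the restart, that paragraph gives an action limited to the visit and then speaks of later infusions, with no exception for subjects whose symptoms recurred. The permanent stop is in the next paragraph, under a different grade, and there is no cross-reference.

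The grade assigned decides what follows. A Grade 2 label leads to premedication and presumes further dosing; a Grade 3 label ends ulocuplumab. A site that keeps the Grade 2 label could conclude that dosing continues in a subject who meets a mandatory stopping criterion. Two sites could also handle and code the same event differently, and that would carry into the worst-grade and discontinuation tables in SAP Sections 7.6.3 and 7.6.4.

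The stake is subject safety and consistent safety data. The CR/CRi analysis is unaffected: SAP Section 7.5.1 bases the final rate on all randomized subjects.

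**Working it through.** The plan states no figure on this point, so the check is a comparison of texts, followed by the little arithmetic the documents allow.

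**The two paragraphs of Section 6.7**

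1. Printed Grade 2 covers a reaction that needs therapy or interruption and responds promptly. Recurrence is not part of that description.
2. Restart is conditional on resolution ("restart the infusion at 50% of the original infusion rate when symptoms resolve").
3. Symptoms that return after restart therefore follow an improvement.
4. "recurrence of symptoms following initial improvement" is printed as a Grade 3 item.
5. The Grade 3 action is permanent. The Grade 2 action for recurrence is limited to the visit.

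| | Grade 2 paragraph | Grade 3/4 paragraph and stopping rules |
|---|---|---|
| Event | Symptoms return after restart | Symptoms return after improving |
| Action | No more ulocuplumab at that visit | Ulocuplumab stopped permanently |
| Later infusions | Premedication recommended | None |
| Instruction to regrade | None | Not applicable |

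Section 4.6.1.1 is worded for study treatment and Table 4.6.1.2-1 for ulocuplumab. On either wording ulocuplumab stops.

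**What further dosing would mean.** Section 4.4 schedules infusions on Days 1, 8 and 15 of Cycles 1 and 2, then Days 1 and 8.

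- Infusions in Cycles 1–2: 2 × 3 = 6, so 6 − 1 = 5 remain after Cycle 1 Day 1, then 2 per cycle.
- Day 1 to Day 8 is 7 days. With the −1/+3 day window in Section 4.6.1.2, the next infusion falls 7 − 1 = 6 to 7 + 3 = 10 days later.

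**Context on frequency.** Section 6.7 reports, at a 17-Feb-2014 cut-off, 1 AML + 3 CLL + 1 DLBCL = 5 subjects with infusion reactions of 86 in CA212001, and 2 of 42 in CA212002.

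- (5 + 2) / (86 + 42) = 7/128 = 5.5%, Clopper-Pearson 95% CI 2.2% to 10.9%.
- Applied to the 80 planned combination-arm subjects: 80 × 7/128 = 4.4 any-grade reactions.

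Section 6.7 gives no grades for these 7. Section 1.5 reports a single Grade 3 reaction in a DLBCL subject in CA212001, probably the one DLBCL case counted here, although Section 1.5 gives no cut-off date for it. The documents do not say how many reactions were Grade 2, restarted and then recurred, so no share is assumed.

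**The case against.** The strongest reply is that the two instructions are compatible: stopping for the visit is the immediate bedside step, and permanent discontinuation follows once the event is graded. A site can satisfy both. The premedication sentence can be read as general advice after any Grade 2 reaction. The stopping rule appears in several places, sites are told to grade by CTCAE v4.03, and Section 4.6.1.2 sends discontinuation questions to the Medical Monitor. All of this stands, and it lowers the risk. It does not remove the gap, because the Grade 2 paragraph neither gives that sequence nor refers to it, and a site that sees no question will not ask one. Section 6.7 also says its treatment recommendations may be adapted locally, but that does not override the separate criterion in Section 4.6.1.1.

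A second reply is that the Grade 3 list is headed as a severe reaction, so a mild recurrence might remain Grade 2. The text does not settle this. That is a reason to state the rule, and it is why the conflict is put as one on the printed wording.

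A reader might infer more than the documents support:

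- **That the protocol orders re-dosing after a recurrence.** It does not. This is an inference from limiting the stop to one visit and then turning to later infusions.
- **That the schedule forces re-exposure on Day 8 because Cycle 1 delays are barred.** Section 4.6.1.2 treats a dose not given in its window as missed and skipped, and Section 3.5 lets the investigator stop treatment.
- **That 7/128 caps the number at risk.** It is an observed rate in other studies with mixed diseases. Neither it nor its interval bounds what happens at 800 or 1000 mg with LDAC.
- **That the 1000 mg safety review is wholly untouched.** Section 5.3.1 excludes Grade 3 infusion reactions from DLTs, so the DLT count does not rise. But the same section counts the assessment period as completed only when all Cycle 1 doses are given, DLT cases aside.

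**Conclusion.** The concern holds as an internal conflict in Section 6.7. On the protocol's printed wording, recurrence after restart is a Grade 3 event requiring permanent discontinuation, while the paragraph a site would be following limits the action to the visit and does not lead to that rule. This is a statement at odds with a mandatory criterion elsewhere, not merely a missing detail.

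The number of subjects affected is unknown and probably zero to a few. The case for acting rests on the possible consequence for an individual subject and on how cheap the correction is, not on frequency. The conclusion assumes that the printed Grade 3 item applies to any recurrence after improvement; if the sponsor intends it only for severe recurrences, the protocol needs to say so. Confidence is moderate because of that ambiguity and the safeguards already present.

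**What to change.** In the Grade 2 paragraph of Section 6.7, replace the recurrence sentence with wording such as: *If symptoms recur after restart, stop the infusion and regrade per CTCAE v4.03; recurrence following initial improvement is Grade 3: follow the Grade 3/4 instructions and permanently discontinue ulocuplumab per Section 4.6.1.1.* Limit the later-infusion premedication sentence to Grade 2 reactions without recurrence. If the sponsor wants some recurrences to remain Grade 2, it should define them and exempt them in Section 4.6.1.1 and Table 4.6.1.2-1.

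The cost is one or two sentences in an amendment or administrative letter, with no new data or procedures. The downside is that a few subjects with mild recurrence lose later doses, as the existing rule already implies. A stop in Cycle 1 for a Grade 3 infusion reaction is not a DLT, but it leaves that subject without a completed DLT assessment period. This matters if the subject is among the first 6 at 1000 mg, so the safety review should state how such a subject is counted.
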